2.2.1 Randomization and drug dispensing irregularities

Randomization and drug-dispensing irregularities occur whenever:

- A randomization is not in accordance with the protocol-defined randomization method, such as a) an ineligible patient is randomized, b) a patient is randomized based on an incorrect stratum, c) a patient is randomized twice, or d) in a dynamic randomization scheme the treatment assignment is, in fact, not random, due to a computer program error.

OR

A patient is dispensed an IMP kit not allocated by the protocol-defined randomization, such as a) a patient at any time in the study is dispensed a different treatment kit than as randomized (which may or may not contain the correct-as-randomized IMP), or b) a nonrandomized patient is treated with IMP reserved for randomized patients.

Randomization and drug-dispensing irregularities will be monitored throughout the study and reviewed on an ongoing basis.

All randomization and drug-dispensing irregularities will be documented in the clinical study report. If the number of irregularities is large enough to make a tabular summary useful, the irregularities will be categorized and summarized among randomized patients (number and percentages). Nonrandomized, treated patients will be described separately. Listings with additional, relevant details will be provided in appendices.

Randomization and drug-dispensing irregularities to be prospectively identified include but are not limited to:

Randomization and drug allocation irregularities
Kit dispensation without IRT transaction
Erroneous kit dispensation
Kit not available
Randomization by error
Patient randomized twice
Stratification error
Patient switched to another site

2.3 ANALYSIS POPULATIONS

Patients treated without being randomized will not be considered randomized and will not be included in any efficacy population.

The randomized population includes any patient who has been allocated to a randomized treatment regardless of whether the treatment kit was used.

For any patient randomized more than once, only the data associated with the first randomization will be used in any analysis population. The safety experience associated with any later randomization will be assessed separately.

The safety experience of patients treated and not randomized will be reported separately, and these patients will not be in the safety population.

2.3.1 Efficacy populations

Efficacy analyses will be based on the treatment group allocated by the IRT according to the randomization schedule at Randomization Visit (as randomized), irrespective of the treatment actually received.

2.3.1.1 *Intent-to treat population*

Efficacy analyses will be based on the ITT population, defined as all randomized patients irrespective of compliance with the study protocol and procedures. Patients will be analyzed for efficacy according to the treatment group to which they are randomized.

2.3.1.2 *CGM sub-study population*

The CGM sub-study population will include all patients from the ITT population (see [Section 2.3.1.1](#)), who met all eligibility criteria for inclusion into the CGM sub-study.

2.3.2 Safety population

Safety analyses will be based on the safety population, defined as all randomized patients who receive at least 1 dose of double-blind IMP (regardless of the amount of treatment administered). Patients will be analyzed for safety analyses according to the treatment actually received.

In addition:

- Non-randomized but treated patients will not be part of the safety population, but their safety data will be presented separately.
- Randomized patients for whom it is unclear whether they took the study medication will be included in the safety population as randomized.

- When a patient is exposed to both sotagliflozin and placebo, the patient will be analyzed in the appropriate sotagliflozin group (depending on the treatment kit taken [400 mg or 200 mg]).
- When a patient is exposed to both sotagliflozin 400 mg (treatment kit) and 200 mg (treatment kit), the patient will be analyzed in the sotagliflozin 200 mg group.
- Randomized patients will be excluded from the safety population only if there is documented evidence (ie, all study dates recorded as no medication taken) that patients have not taken the study medication. If a patient is dispensed double-blind IMP and is lost to follow-up without any documented evidence, the patient will be considered exposed

2.3.3 PK population

For PK analyses, the PK population is defined as all safety patients who contribute with at least 1 valid plasma concentration of sotagliflozin or its 3-O-glucuronide metabolite. The PK data will be analyzed according to the treatment actually received (see [Section 2.3.2](#)).

2.4 STATISTICAL METHODS

2.4.1 Demographics and baseline characteristics

Continuous data will be summarized using the number of available data, mean, standard deviation (SD), median, minimum, and maximum for each treatment group. Categorical and ordinal data will be summarized using the number and percentage of patients in each treatment group.

Parameters will be summarized on the randomized population analyzed in the treatment group to which they were randomized. Analyses for the safety population will be included in the appendices if the size of the safety population is different (>10%) from the size of that in the primary analysis population for any treatment group.

Parameters described in [Section 2.1.1](#) will be summarized by treatment group and overall (pooled across treatment groups) using descriptive statistics.

P-values on the treatment difference for the demographic and baseline characteristic data will not be calculated.

In general, no specific description of the safety parameters will be provided at baseline. If relevant, the baseline values will be described along with each safety analysis.

In general, no specific description of the efficacy parameters will be provided at baseline. If relevant, the baseline values will be described along with each efficacy analysis.

2.4.2 Prior or concomitant medications

The prior, concomitant and posttreatment medications will be presented in the randomized population for each treatment group (and overall for the summary of prior medications), using counts and percentages. No statistical test for the between-group difference will be performed.

Medications will be summarized by treatment group according to the WHO-DD dictionary, considering the first digit of the anatomical therapeutic chemical (ATC) class (anatomic category) and the first 3 digits of the ATC class (therapeutic category). A given medication may be classified in more than 1 ATC class. All ATC codes corresponding to a medication will be summarized, and a patient will be counted once in each ATC category (anatomic or therapeutic) linked to the medication. Therefore, a patient may be counted several times for the same medication.

Prior medications will be presented by anatomic and therapeutic categories and sorted by decreasing frequency of ATC based on the overall incidence across treatment groups. In case of equal frequency regarding ATCs (anatomic or therapeutic categories), alphabetical order will be used.

Concomitant and posttreatment medications will be presented by anatomic and therapeutic categories and sorted by decreasing frequency of ATC based on the incidence in the sotagliflozin 400 mg group. In case of equal frequency regarding ATCs (anatomic or therapeutic categories), alphabetical order will be used.

Antidiabetic medication will be presented separately by pharmacological class, chemical class and standardized medication name.

2.4.3 Extent of investigational medicinal product exposure and compliance

The extent of IMP exposure and compliance will be assessed and summarized by actual treatment within the safety population (Section 2.3.2).

2.4.3.1 Extent of investigational medicinal product exposure

The extent of IMP exposure will be assessed by the duration of IMP exposure.

Duration of IMP exposure is defined as last dose date of double-blind IMP – first dose date of double-blind IMP + 1 day, regardless of unplanned intermittent discontinuations (see Section 2.5.3 for calculation in case of missing or incomplete data).

Duration of IMP exposure will be summarized descriptively as a quantitative variable (number of patients exposed, mean, SD, median, minimum, and maximum). In addition, duration of treatment exposure will also be summarized categorically by numbers and percentages for each of the following categories and cumulatively according to these categories:

- 1 to 28 days,
- 29 to 56 days,
- 57 to 84 days,
- 85 to 126 days,
- 127 to 182 days,
- 183 to 364 days,
- >364 days.

Additionally, the cumulative duration of treatment exposure will be provided, defined as the sum of the duration of treatment exposure for all patients, and will be expressed in patient years.

Number and percentages of patients by final dose at the end of the treatment will also be presented by each treatment group.

2.4.3.2 Compliance

A given administration will be considered noncompliant if the patient did not take the planned dose of treatment as required by the protocol. No imputation will be made for patients with missing or incomplete data.

Percentage of compliance for a patient will be defined as the number of days that the patient was compliant divided by the total number of days that the patient was planned to take during the treatment epoch defined in [Section 2.1.4](#) (ie, from the first date to the last date of double-blind IMP administration).

Above-planned dosing percentage for a patient will be defined as the number of days that the patient took a higher dose than planned divided by the total number of days that the patient was planned to take during the treatment epoch.

Under-planned dosing percentage for a patient will be defined as the number of days that the patient took a lower dose than planned divided by the total number of days that the patient was planned to take during the treatment epoch.

Treatment compliance, above-planned, and under-planned dosing percentages will be summarized descriptively as quantitative variables (number, mean, SD, median, minimum, and maximum). The percentage of patients whose compliance is <80% will be summarized. In addition, numbers and percentages of patients with at least 1 day above-planned dose administration will be

provided, as well as numbers and percentages of patients with (0, 20%], and >20% of days under-planned dose administrations.

Cases of overdose (see study protocol for further details) will constitute AEs/SAEs and be analyzed as such. More generally, dosing irregularities will be listed in [Section 2.2.1](#).

2.4.4 Analyses of efficacy endpoints

Efficacy analyses will be performed on the ITT population using the efficacy assessments collected during the study, including those obtained after IMP discontinuation or introduction of rescue therapy, unless otherwise specified.

Missing data for efficacy analyses is identified through steps described in [Section 2.5.4](#).

2.4.4.1 Analysis of primary efficacy endpoint(s)

The statistical tests will be two-sided tests at a nominal 5% significance level.

Primary analysis

The primary efficacy endpoint of change in HbA1c from baseline to Week 18 will be analyzed by an Analysis of Covariance (ANCOVA) model using HbA1c values measured at baseline and Week 18 (observed or imputed). The missing data at endpoint will be imputed by multiple imputation (MI) methods as detailed below. To be concise, the following texts related to imputation are generalized to accommodate primary as well as continuous secondary efficacy endpoints.

Missing endpoint data at Week 18 (or Week 12 for SBP or Week 52 for HbA1c and BW) visit will be imputed using a model built separately in each treatment group and estimated from the patients in the same treatment group who prematurely discontinue the IMP before the Week 18 (or Week 12 for SBP or Week 52 for HbA1c and BW) visit but have the measurement for the endpoint (retrieved dropouts). The imputation model will include the randomization strata and the corresponding baseline value. In cases of non-convergence during the imputations, the offending stratum will be identified and then will be dropped from the model. Considering that the number of patients in each treatment group who discontinue the IMP but have the measurement for the endpoint is expected to be small, a simple imputation model based on regression will be used with baseline measurement included as the predictor. This will serve as the primary model of imputation for missing data should sampling criteria be satisfied (see below).

An alternative (back-up) imputation method will be used if the number of patients who prematurely discontinue the IMP before the Week 18 (or Week 12 for SBP or Week 52 for HbA1c and BW) visit but have the measurement for the endpoint is <5 in any treatment groups (ie, not sufficient retrieved dropouts to support the imputation method described above). This criterion will be assessed for each primary or continuous secondary efficacy endpoint.

In the back-up imputation method, missing post-baseline endpoint values at Week 18 (or Week 12 for SBP or Week 52 for HbA1c and BW) will be imputed by washout multiple imputation (MI) method under the missing not at random (MNAR) framework.

Missing endpoint data at Week 18 (or Week 12 for SBP or Week 52 for HbA1c and BW) in the sotagliflozin group(s), as well as in the placebo group are imputed from a model estimated from patients in the placebo group who have the endpoint data available.

For patients in the sotagliflozin 400 mg and 200 mg groups with missing data at Week 18 (or Week 12 for SBP or Week 52 for HbA1c and BW), their missing values will be imputed using observed baseline and the observed primary endpoint data from placebo completers; no intermittent values from either placebo or the active treatment groups will be used.

For placebo patients, missing data will be imputed based on the placebo group data. Intermittent observed values will be used while imputing missing values at Week 18 (or Week 12 for SBP or Week 52 for HbA1c and BW). In cases that a non-monotone missing data pattern occurs at the intermediate visits, these data points will be first imputed in the placebo group using the Markov Chain Monte Carlo (MCMC) option in PROC MI to achieve a monotone missing pattern for all placebo patients. The Week 18 (or Week 12 for SBP or Week 52 for HbA1c and BW) endpoint values will be subsequently imputed from the multiple copies of the original dataset where each copy will have a monotone missing pattern.

The imputation models for the washout MI method will include the randomization strata and the corresponding baseline value. Missing data will be imputed using the regression method. In cases of non-convergence during the imputations, especially for the MCMC application in the placebo non-monotone datasets, graphical measures (eg, trace and autocorrelation plots) will be used to identify the offending variable and once detected, that variable(s) will be dropped from the model and the imputations will be re-run. These re-run models will use the same seed number and number of imputations as used in the original models.

Using either imputation method, missing endpoint data will be imputed multiple times to generate multiple data sets with complete data. The change from baseline to Week 18 will be derived from observed and imputed HbA1c value at Week 18. Each of the complete datasets after the imputation will be analyzed by the ANCOVA model with treatment groups (sotagliflozin 400 mg, sotagliflozin 200 mg, placebo), randomization strata of Week -1 HbA1c ($\leq 8.5\%$, $> 8.5\%$), randomization strata of Week -1 SBP (< 130 mmHg, ≥ 130 mmHg), randomization strata of sulfonylureas use at Week -1 (yes, no), and country as fixed effects, and baseline HbA1c value as a covariate. Results from each complete dataset will be combined using Rubin's rule to provide the adjusted mean change in HbA1c from Baseline to Week 18 for each treatment group, as well as the between-group difference (comparing sotagliflozin 400 mg, 200 mg vs placebo) and the 95% confidence interval (CI).

Sensitivity analyses

Tipping point analysis based on the same MI method as applied to the primary analysis will be performed to examine the robustness of the results from the primary analysis. Patients who were randomized to sotagliflozin groups and had no HbA1c data at Week 18 will be given a penalty. The penalty will be gradually increased to evaluate at which level the conclusion of the analyses in terms of statistical significance is changed (see below). The tipping point is the penalty level, at which the magnitude of efficacy reduction in patients without HbA1c data at Week 18 creates a shift in the treatment effect of sotagliflozin 400 mg from being statistically significantly better than placebo to a non-statistically significant effect. LS mean difference between sotagliflozin 400 mg and placebo and its associated p-value will be provided for each penalty level. The steps to perform the tipping point analysis comparing sotagliflozin 400 mg versus placebo are as follows:

1. Missing data will be imputed using the same MI method as applied to the primary analysis,
2. The imputed HbA1c value at Week 18 in the sotagliflozin group will be penalized by adding a penalty δ (eg, $\delta = 0.1\%$) in each complete dataset,
3. Change from baseline at Week 18 in HbA1c will be analyzed using the same ANCOVA model as specified in the primary analysis in each complete dataset,
4. Results will be combined across complete datasets using Rubin's rule,
5. Steps 2 to 4 will be repeated with incremental penalty at δ (ie, $\delta, 2\delta, 3\delta, \dots$) until the p-value for treatment effect of sotagliflozin 400 mg compared to placebo estimated in Step 4 is >0.05 .

The above tipping point analysis will be replicated to examine the robustness of the treatment effect of sotagliflozin 200 mg (ie, adding penalty to the sotagliflozin 200 mg group instead of sotagliflozin 400 mg group).

The tipping point analysis will be performed only if the corresponding primary or secondary endpoint (change from baseline to Week 18 in HbA1c comparing sotagliflozin 400 mg vs placebo, or comparing sotagliflozin 200 mg vs placebo) is statistically significant at $\alpha = 0.05$ (2-sided).

In addition, if the retrieved dropout imputation is applied to the primary analysis, the analysis based on the washout (ie, the backup imputation method) will be presented as a sensitivity analysis.

To investigate the impact of randomization stratification error of HbA1c at Week -1 ($\leq 8.5\%$, $>8.5\%$), the following sensitivity analyses will be performed for the primary or secondary endpoint (change from baseline to Week 18 in HbA1c comparing sotagliflozin 400 mg vs placebo or comparing sotagliflozin 200 mg vs placebo):

- The same model as described in the primary analysis will be performed by excluding those patients with randomization stratification error regarding HbA1c at Week -1 ($\leq 8.5\%$, $>8.5\%$).

- The same model with the same MI method as described in the primary analysis will also be performed by replacing randomization strata of HbA1c ($\leq 8.5\%$, $>8.5\%$) at Week -1 from IRT with the actual strata calculated based on HbA1c value ($\leq 8.5\%$, $>8.5\%$) at Week -1 from central lab in both imputation model and analysis model.

Patients in this study have undergone sampling for plasma levels of sotagliflozin and its main active metabolite in order to perform population PK analysis. Patients may be identified who have no detectable levels of active study drug or metabolite in their samples (ie, Below Lower Limit of Quantification or BLLOQ). When sample analysis has been completed and the study has been unblinded, explanations for some of these patients may be found: known non-compliance or sampling occurring after treatment had been discontinued. In other cases, drug intake history relative to the randomization assignment may not be fully explained. The ITT-based analyses specified in this document provides for a conservative assessment of the efficacy data should patients have been subjected to these unexplained non-compliance findings or PK ‘anomalies’. To provide a broader perspective on the impact of these apparent errors in compliance, additional sensitivity analyses of the primary efficacy endpoint and continuous efficacy endpoints may be conducted. The need to perform such analyses, their specifics, and results will be provided in the Clinical Study Report (CSR), if applicable. The analysis methods applied to the patient subpopulations defined by the occurrence of the PK anomalies (eg., exclusion of patients with PK anomalies from the ITT dataset) will include the ANCOVA model using the retrieved dropout and/or washout MI methods previously specified in this section.

Assessment of treatment effect by subgroup

Descriptive analyses will be performed on the primary endpoint to summarize the treatment effects across subgroups defined by the following Baseline or Screening factors:

- Race (White, Black or African American, Asian, Other) (any race groups with fewer than 5 patients may be combined with “Other” category as appropriate),
- Ethnicity (Hispanic, Not Hispanic),
- Age group (<50 , ≥ 50 to <65 , ≥ 65 years) (any category with fewer than 5 patients may be combined with another category as appropriate),
- Gender (Male, Female),
- Baseline BMI level (<30 , ≥ 30 kg/m²),
- Baseline HbA1c ($\leq 8.5\%$, $>8.5\%$),
- Baseline SBP (<130 mmHg, ≥ 130 mmHg),
- Sulfonylurea use at Week -1 (yes, no),
- Baseline eGFR (≥ 30 to <60 mL/min/1.73m² [Moderate decrease in GFR], ≥ 60 to <90 mL/min/1.73m² [Mild decrease in GFR], and ≥ 90 mL/min/1.73m² [Normal])
- Duration of diabetes (<10 , ≥ 10 years)

- Country.

The treatment effects (sotagliflozin 400 mg versus placebo and sotagliflozin 200 mg versus placebo) across the subgroups defined for each of these factors will be estimated for the change from Baseline to Week 18 in HbA1c in the ITT population, and using the same MI method as applied to the primary analysis. The ANCOVA model will include treatment groups (sotagliflozin 400 mg, sotagliflozin 200 mg, placebo), randomization strata of Week -1 HbA1c ($\leq 8.5\%$, $> 8.5\%$), randomization strata of Week -1 SBP (< 130 mmHg, ≥ 130 mmHg), randomization strata of sulfonylureas use at Week -1 (yes, no), subgroup factor, treatment-by-subgroup factor, and country as fixed factors and using baseline HbA1c value as a covariate. The adjusted estimates of treatment mean differences (sotagliflozin 400 mg versus placebo) with standard error (SE) and 95% CIs will be provided as appropriate across the subgroups. A graphical presentation of the results (ie, forest plot) will also be provided.

In the case that the subgroup factor is identical or similar to a randomization strata factor (eg, baseline HbA1c or baseline SBP category or Sulfonylurea use at Week -1), only the subgroup factor (as a single factor or an interaction term) will be included in the model in order to avoid the issue of collinearity in the analysis. The corresponding strata factor will not be included in the model.

Summary statistics at scheduled visits

Summary statistics (for screening value, baseline value, observed post-baseline value and its changes from baseline) at scheduled visits will be provided for each treatment group. The summary will include the number of observations, mean, SD, SE, minimum, median, and maximum. Graphical presentations will also be used to examine trends over time using mean values (\pm SE) and mean changes from baseline (\pm SE) at each of the scheduled visits.

Similar presentations will be provided excluding measurements after rescue therapy during the 52-week entire treatment period.

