8.3.2 Randomization code breaking during the study

In case of an AE, the code should only be broken in circumstances when knowledge of the IMP is required for treating the patient.

Code breaking can be performed at any time by using the proper module of the IRT and/or by calling any other phone number provided by the Sponsor for that purpose. Code breaking can be performed by a local study Investigator, sponsor physician or healthcare professional with direct responsibility for patient care. If the blind is broken, the Investigator should document the date, time of day, and reason for code breaking. The identity of the unblinded personnel, how the code was broken, and the treatment kit number should also be recorded. The Sponsor should also be informed. If the code is broken by the Investigator (or other medical doctor in emergency situation), the patient must be withdrawn from IMP administration.

Refer to [Section 10.5](#) for suspected unexpected serious adverse reaction (SUSAR) unblinding by the Sponsor.

Randomization code breaking will also be performed during the analysis of the Pharmacokinetic plasma concentration samples. Only the Project manager and lead scientist at the Bioanalytical laboratory will have access to the randomization code to allow for the sorting of the sotagliflozin plasma samples. The Bioanalytical lab and responsible personnel will follow the standard procedures (SOP) to ensure the protection of the blind within the Sponsor's clinical team. The randomization code or the individual analytical results will not be disclosed to any clinical team personnel prior to the database lock.

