11 STATISTICAL CONSIDERATIONS

11.1 DETERMINATION OF SAMPLE SIZE

The sample size/power calculations were performed based on the primary endpoint. Assuming a common standard deviation (SD) of 1.2% and using a 2-sided test at a 0.05 α -level, 280 patients in the sotagliflozin 400 mg arm and 140 patients in the placebo arm will provide at least 95% power to detect a treatment difference of 0.5% in mean HbA1c change from Baseline to Week 18 between sotagliflozin 400 mg and placebo.

A sample size of 140 patients in the sotagliflozin 200 mg arm and 140 patients in the placebo arm will provide 80% power to detect a treatment difference of 0.4% in mean HbA1c change from Baseline to Week 18 between sotagliflozin 200 mg and placebo (SD 1.2%; 5% significance level 2-sided).

The total sample size will be 560 patients to be randomized (280 patients in the sotagliflozin 400 mg arm; 140 patients in the sotagliflozin 200 mg arm; 140 patients in the placebo arm).

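### The optional PK-anomaly analysis may exclude patients with undetectable drug, which can remove only sotagliflozin patients, under a rule left open until after unblinding

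*SAP*

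**What the plan says.** The sensitivity-analysis part of SAP 2.4.4.1 describes patients with no measurable sotagliflozin or metabolite. It places the search for explanations late: "When sample analysis has been completed and the study has been unblinded". Some cases may prove to be known non-compliance or sampling after treatment stopped; others may stay unexplained. Further analyses of the primary and continuous efficacy endpoints are optional, and the SAP adds: "The need to perform such analyses, their specifics, and results will be provided in the Clinical Study Report (CSR), if applicable". The model is fixed (the ANCOVA, with retrieved-dropout imputation, washout imputation or both), and the example of how the subpopulation would be handled is "exclusion of patients with PK anomalies from the ITT dataset". SAP 1.6, Table 2, gives the purpose as checking the robustness of the ITT analyses.

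SAP 2.1.5 and 2.4.6 confine the PK variables to the sotagliflozin group. Protocol 8.3.2 lets the laboratory use the treatment code to sort out the sotagliflozin samples ("Only the Project manager and lead scientist at the Bioanalytical laboratory will have access to the randomization code") and keeps individual results from the clinical team until database lock. Protocol 9.3.1.1 schedules pre-dose samples at Weeks 4, 18, 26 and 52, with none after premature discontinuation.

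**The concern.** The marker works in one direction only. A sotagliflozin patient who takes no tablets can be found by a drug level; a placebo patient who takes no tablets cannot. Excluding on this marker compares sotagliflozin takers with placebo takers and non-takers together, so the comparison is no longer randomized. By contrast, the stratification-error exclusion in the same section rests on a Week -1 criterion that applies equally to all arms.

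The SAP does not say which visits count, how many undetectable samples make an anomaly, whether explained cases count, or which imputation method applies. Those choices would be made when their effect on the result can be seen. If the drug works, the exclusion is expected to raise the estimate, so agreement with ITT would say little about robustness. At stake is how a supportive result in the study report is read.

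**Working it through.** **1. The plan's own figures.** Protocol 11.1: "Assuming a common standard deviation (SD) of 1.2% and using a 2-sided test at a 0.05" level; "280 patients in the sotagliflozin 400 mg arm and 140 patients in the placebo arm"; "at least 95% power to detect a treatment difference of 0.5% in mean HbA1c change from Baseline to Week 18". For the lower dose: "A sample size of 140 patients in the sotagliflozin 200 mg arm and 140 patients in the placebo arm", 80% power for 0.4%.

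With SE = 1.2 x sqrt(1/n1 + 1/n2) and power = Phi(difference/SE - 1.96):
- 400 mg: SE = 1.2 x sqrt(1/280 + 1/140) = 0.124; 0.5/0.124 = 4.03; power 98.1%, which meets the stated minimum of 95%.
- 200 mg: SE = 1.2 x sqrt(2/140) = 0.143; 0.4/0.143 = 2.79; power 79.6%, which agrees with 80%.

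These figures are sound. They serve here only as a scale.

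**2. A model for the exclusion.** Let D be the HbA1c benefit in takers, p the share of non-takers (equal in expectation across arms by randomization) and d the amount by which non-takers do worse whatever the arm. Assume that non-takers get no drug effect and that every non-taker in the active arm is flagged.
- ITT difference = (1 - p) x D.
- Active takers against all placebo = D + p x d.
- Bias against the effect in takers = p x d.

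**3. Assumed ranges.** With p of 5-15% and d of 0-0.5%, the bias runs from 0 (d = 0) to 0.15 x 0.5 = 0.075% HbA1c. That upper end is 0.075/0.124 = 0.60 of the 400 mg standard error.

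**4. Shift from ITT.** Suppose the ITT difference equals the 400 mg design value, so D = 0.50/(1 - p). The last column takes D = 0 and SE = 1.2 x sqrt(1/(280(1 - p)) + 1/140).

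| p | Exclusion estimate, d = 0 | Exclusion estimate, d = 0.5 | p x d at d = 0.5 | Two-sided rejection rate with no drug effect, d = 0.5 |
|---|---|---|---|---|
| 5% | 0.526 | 0.551 | 0.025 | 5.5% |
| 10% | 0.556 | 0.606 | 0.050 | 6.8% |
| 15% | 0.588 | 0.663 | 0.075 | 9.0% |

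For 200 mg, an ITT difference of 0.40 becomes 0.421, 0.444 and 0.471 with d = 0, and 0.446, 0.494 and 0.546 with d = 0.5.

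Two parts should be kept apart. The factor 1/(1 - p) is a change of target, from everyone assigned to those who take the drug. Only p x d is bias. With d = 0 the rejection rate under no drug effect stays at 5.0%; with d below 0 the bias reverses.

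**5. An estimator that keeps everyone.** ITT/(1 - p) returns D without the p x d term. At p = 10%, 0.50/0.90 = 0.556. Treating p as known, the SE rises from 0.124 to 0.124/0.90 = 0.138.

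**The case against.** The strongest reply is that little depends on this analysis. It is optional, and exclusion is only an example. ITT remains the basis for efficacy (SAP 2.4.4), and SAP 2.4.4.1 calls it conservative. The fixed testing sequence in SAP 2.4.4.4 does not include it. The marker, the ANCOVA and the two candidate imputation methods are written down. The access rule in Protocol 8.3.2 is a blinding safeguard, not evidence of data-driven rules. Run-in excludes patients below 80% tablet compliance, which plausibly lowers p. Some anomalies may be dispensing errors, which SAP 2.2.1 lists as a possible irregularity; d could then be near zero.

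All of that stands, and it limits the size and weight of the point. A reader might infer that the plan commits to dropping patients, that it states an active-arms-only rule, or that the primary result is biased. The documents support none of these: the wording is permissive, the one-sidedness follows from what the marker can detect, and the primary analysis keeps all randomized patients.

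The reply does not settle the rest. Naming the marker does not say which samples or cases count, and the only method exemplified loses the randomized comparison.

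**Conclusion.** The concern holds for an optional supportive analysis. Run as exemplified, it can exclude only sotagliflozin patients, under a rule not fixed before unblinding, and it is not a sound check on the robustness of ITT.

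The bias against the effect in takers is 0-0.075% HbA1c under the assumed ranges. The top of that range is 0.075/0.5 = 15% of the 400 mg design difference, and it needs both assumptions at their upper end. A reader might take 15%, or a bias always towards the drug, as established. Neither is: the documents give no value for p or d, and the bias is zero if non-takers have the same prognosis as takers. The rise relative to ITT needs only a drug that works and some flagged patients who got no drug effect. The rejection rates above belong to this analysis alone; the primary test keeps its type I error.

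**What to change.** Before unblinding, amend SAP 2.4.4.1 as follows. No PK results are needed to do so.

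- Define a PK anomaly from scheduled on-treatment samples up to the endpoint visit only: Weeks 4 and 18 for the Week 18 endpoint. A rule using all samples to Week 52 would count a patient with no drug through Week 18 but detectable drug at Week 26 as a taker for the primary endpoint.
- State how many samples must be undetectable, whether explained cases count, and how patients with no eligible sample are classed.
- Fix the imputation method in place of the open choice. Using on-treatment samples only also avoids flagging patients because they were sampled after stopping, which could otherwise remove retrieved dropouts that the imputation model needs.
- Replace the exclusion example with a complier-average estimate for each dose: the ITT difference divided by the proportion of takers in that active arm, with all randomized patients kept. State its assumptions of all-or-none intake and no drug effect in non-takers.
- Label any exclusion analysis that is kept as exploratory and non-randomized, not as a robustness check.

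The cost is SAP wording, one short analysis and a wider interval for the complier estimate (about 11% wider at p = 10%, from 1/0.90).
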